6.5 Concomitant Therapy

N/A

6.5.1 Rescue Therapy

N/A

7 Study Intervention/Experimental Manipulation Discontinuation and Participant Discontinuation/Withdrawal

7.1 Discontinuation of Study Intervention/Experimental Manipulation

If a participant experiences an adverse reaction while using VR, they will be given the option to continue the session viewing the same experiences on a tablet instead. In this case, all remaining study procedures will be completed as indicated by the study protocol.

If a clinically significant finding is identified after enrollment, the investigator or a qualified designee will determine if any change in participant management is needed. Any new clinically relevant finding will be reported as an adverse event (AE).

The data to be collected at the time of study intervention discontinuation will include:

- The reason(s) for discontinuing the participant from the intervention, including documentation of adverse events or tense interpersonal dynamics.

7.2 Participant Discontinuation/Withdrawal from the Study

Participants are free to withdraw from participation in the study at any time upon request.

An investigator may discontinue a participant from the study for the following reasons:

- Significant study intervention non-compliance
- Lost-to-follow up; unable to contact subject
- Any event or medical condition or situation occurs such that continued collection of study data would not be in the best interest of the participant
- The participant meets an exclusion criterion (either newly developed or not previously recognized) that precludes further study participation.

The reason for participant discontinuation or withdrawal from the study will be recorded on the Case Report Form (CRF). Subjects who sign the informed consent form and are randomized but do not receive the study intervention may be replaced. Subjects who sign the informed consent form, and are randomized and receive the study intervention, and subsequently withdraw, or discontinued from the study will not be replaced.

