1.2 Schema

Note: Because participation in the intervention required both members of the dyad, if one member chose to withdraw during the intervention phase, the entire dyad was discontinued. However, after the

[figure not shown]
intervention phase was completed, individual members could withdraw independently, allowing the other member to continue participating in post-intervention and follow-up surveys. **Attrition prior to the end of the intervention phase:** 20 dyads + 2 individuals (out of 372 consented) = **42/372**, or **11.3%**. **Total attrition over the course of the trial:** 20 dyads + 12 individuals = **52/372**, or **13.9%**.

Participant retention was monitored throughout the study, and reasons for attrition were recorded. Attrition was categorized into the following predefined groups: (1) **Withdrew consent** (participants voluntarily discontinued for personal reasons, such as time burden or loss of interest); (2) **Adverse events** (participants discontinued due to health or safety reasons – physical or psychological – including withdrawal by the study investigator); (3) **Health-related limitations** unrelated to the intervention that prevented continued participation (e.g., hospitalization, fall, cancer treatment); (4) **Protocol deviations or ineligibility** identified post-randomization (e.g., undisclosed history of seizure); (5) **Partner withdrawal**, where the dyadic nature of the study required discontinuation when a study partner withdrew; (6) **Death** during the study period unrelated to the intervention; and (7) **Lost to follow-up**, where participants became unreachable and did not complete one or more follow-up assessments.

Participants who missed one or more survey assessments but later completed subsequent surveys were classified as having **intermittent missing** data. These cases were not considered lost to follow-up and were retained in all analyses for which valid data were available. Reasons for missed assessments were not always reported but were presumed to reflect temporary nonresponse rather than formal withdrawal or disengagement from the study. In addition, in rare cases, survey data were lost due to administrative or technical errors despite participant completion. These cases were treated as **missing (administrative)** in the relevant analyses.

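### No T6–T8 surveys are provided for people whose participation is ended for non-compliance or a newly met exclusion criterion, or for a partner left behind mid-intervention

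*Combined protocol and SAP*

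**What the plan says.** Visit numbers follow section 1.3: T6 is the post-study survey, T7 the 1-month and T8 the 3-month follow-up.

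- **Section 7.2** introduces its list with "An investigator may discontinue a participant from the study for the following reasons". Two of the reasons are "Significant study intervention non-compliance" and "The participant meets an exclusion criterion (either newly developed or not previously recognized) that precludes further study participation". Another covers situations in which "continued collection of study data would not be in the best interest of the participant".
- **Section 7.1**, on stopping the intervention, says that "all remaining study procedures will be completed as indicated by the study protocol". This applies only to someone who has an adverse reaction in VR and continues on a tablet. The only data item it lists at discontinuation is the reason.
- **Section 1.2** states that "if one member chose to withdraw during the intervention phase, the entire dyad was discontinued". It has an attrition category for partners, "where the dyadic nature of the study required discontinuation when a study partner withdrew". After the intervention phase the rule changes: members may leave separately, "allowing the other member to continue participating in post-intervention and follow-up surveys".
- **Section 8.2**, item 11, lets staff discuss removal from the study with the family after suspected VR-related hallucinations or seizures.
- **Section 5.5** has residents surveyed in person and adult children online at follow-up.
- **Sections 9.3 and 9.4.1** set an intention-to-treat primary analysis that does not depend on completing the intervention. Maximum likelihood is the named method for missing data.

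**The concern.** The sessions need both members of a dyad, but the surveys do not. Section 1.2 accepts this once the intervention phase is over. Before that point, the plan has no route by which a willing person who has stopped sessions, or whose partner has left, goes on to T6–T8.

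Section 6.1.2 places the primary measures at baseline and three post-intervention points. For someone with a baseline who is stopped during T2–T5, all three post-intervention assessments are missing and the model must infer them. For most constructs it has the baseline and any weekly surveys to work from. For thriving, section 1.3 schedules no weekly measurement, so only the baseline is available.

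Maximum likelihood is adequate if the earlier data explain the later differences. If people stopped for poor compliance, a new symptom or a partner's departure do better or worse later in ways the earlier data do not show, it does not correct for that. If this differs by arm, the treatment comparison is biased. Some routes are specific to VR (the tablet option and section 8.2, item 11), so imbalance is plausible, though not shown.

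**Working it through.** **1. Reproduce the plan's attrition figures (section 1.2).**
- Before the end of the intervention phase: (2 × 20 + 2)/372 = 42/372 = 11.3%, as stated.
- Whole trial: (2 × 20 + 12)/372 = 52/372 = 13.98%, or 14.0%. The document prints 13.9%; the counts agree.
- Section 9.2 assumes about 15%, so attrition is within plan.
- Dyads: 372/2 = 186. Dyads lost early: 20/186 = 10.8%. They account for 40 of the 42 early losses.

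**2. How many people could follow-up reach?** The text splits the 20 dyads by neither reason nor arm; the schema figure is not available and may do so. None is shown to fall under the two section 7.2 reasons, and some may have left before baseline, outside the section 9.3 set. Where a member withdrew consent, at most one partner per dyad remains, so the range is 0 to 20 people. Assume that all 20 losses began with one member's withdrawal:
- Half by residents and half by adult children: 20/2 = 10 remaining partners of each type.
- Split evenly by arm: 10/2 = 5 per arm and member type.

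**3. Effect on the arm difference.** Take one member type and assume 186/2 = 93 per arm. Suppose k people in one arm differ at T6–T8 by δ from what the model infers, and those in the other arm do not. The arm difference then moves by δ × k/93. With an assumed δ = 0.5 SD:

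| k in one arm | Shift (SD) | Share of d = 0.2 |
|---|---|---|
| 0 | 0 | 0% |
| 5 | 0.5 × 5/93 = 0.027 | 13% |
| 10 | 0.5 × 10/93 = 0.054 | 27% |
| 20 | 0.5 × 20/93 = 0.108 | 54% |

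The k = 5 row is what follow-up could address under the even split in step 2. The k = 10 row counts every early-stopped person of one member type, with the 20 dyads split evenly by arm. The k = 20 row puts all 20 dyads in one arm. Both of these rows include people who themselves withdrew. Equal numbers with equal departures in both arms cancel.

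**The case against.** The case against has five parts.

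**Reach.** Section 7.2 is permissive, and its exclusion reason covers only criteria that preclude further participation. Section 6.4 reschedules missed sessions, and the tablet option keeps people in the study. Section 1.2 also counts 2 people lost singly before the intervention phase ended, so a whole-dyad stop did not follow every time; the text does not say why. All of this stands, and the number reached may be very small. None of it supplies the missing provision.

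**Timing.** Section 1.2 reports attrition over the whole trial in the past tense. If collection has finished, new wording recovers nothing here. This stands, and it decides which part of the fix applies.

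**Consent and pressure.** Under section 10.1.1.2, consent for a resident with dementia is also obtained from the participating adult child and from any separate legal guardian. If that adult child leaves, whether the resident may continue alone is a consent question. Section 2.3.1 names pressure to remain as a risk, and section 5.5 commits staff to avoiding it. This stands, and the fix has to allow for it.

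**Size.** A reader might take 27% or 54% of the planning effect as the bias that follow-up would remove. The documents do not support that. Those figures count early-stopped people whether or not they could be followed, and the 0.5 SD is an assumption with no source in the plan.

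**Contradiction.** A reader might also infer that section 7.2 contradicts the intention-to-treat statement. It does not. Sections 9.3 and 9.4.1 say who is analysed and in which group; they do not govern data collection. What exists is a gap in collection, which leaves the analysis relying on inferred values.

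**Conclusion.** The point holds as a cheap improvement. The plan lets study participation end, not only sessions, for two reasons that do not in themselves prevent someone from answering a survey, and it stops the remaining partner when one member withdraws mid-intervention. It provides no T6–T8 surveys afterwards for those willing and able.

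The omission is clear from the text; its consequence is not. The number affected is unknown and may be zero. About 0.027 SD (13% of d = 0.2) is a conditional illustration. It rests on all 20 early dyad losses starting with one member's withdrawal, an even split by member type and arm, 93 per arm, every reachable partner in one arm departing by 0.5 SD, and no departure in the other arm. Anyone stopped by an investigator who would still answer surveys would add to the number reached; the text gives no count.

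A reader might infer that the 20 lost dyads show the rule doing damage, or that the trial lost power through it. Neither is supported: no loss is tied to the section 7.2 reasons, and attrition of 14.0% is within the assumed 15%. The issue is possible bias.

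**What to change.** **If data are still being collected.** For the two section 7.2 reasons (non-compliance and a newly met exclusion criterion), and for the remaining partner in the section 1.2 dyad note, stop the technology sessions only. Still offer T6, T7 and T8 on the original calendar, except where:
- that person withdraws consent;
- for a resident with dementia, the consent given by the adult child or legal guardian is withdrawn or not reconfirmed; or
- continued data collection is not in the person's interest, the ground that section 7.2 already contains.

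State that the offer is made without pressure. This takes no position on when sessions should stop.

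The cost is protocol wording, a consent check, and up to three existing surveys per person reached. Resident surveys are in person, so some will be unsuitable.

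**If data collection is over.** Leave the wording and add one delta-adjusted sensitivity analysis by arm. Multiply impute the T6–T8 values of living discontinued participants, then shift them from 0 to 0.5 SD in the unfavourable direction for each outcome, separately in each arm. Handle deaths separately, and report whether the conclusion changes over the range. The cost is one further analysis of data already held.

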7.3 Lost to Follow-Up

A participant will be considered lost to follow-up if he or she fails to return for 1 scheduled visit and study staff are unable to contact the participant after at least 3 attempts.

The following actions must be taken if a participant fails to attend their required virtual study visit:

- The investigator or research assistant will attempt to contact the participant, reschedule the missed visit within the next week, and emphasize the importance of maintaining the assigned visit schedule and ascertain if the participant wishes to and/or can continue in the study.
- Before a participant is deemed lost to follow-up, the investigator or research assistant will make every effort to regain contact with the participant (3 telephone calls or texts and emails).
- Should the participant continue to be unreachable, he or she will be considered to have withdrawn from the study with a primary reason of lost to follow-up.

8 Study Assessments and Procedures

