4.3 Justification for Intervention

The selected mode of intervention delivery—weekly ~20-minute VR sessions—was informed by the success and findings of our Phase I study, which demonstrated feasibility and positive engagements with this schedule. Limiting sessions to approximately 20 minutes helps mitigate potential adverse effects of extended VR exposure, such as eye fatigue, while ensuring participants have sufficient time to meaningfully engage with the experience.

This intervention schedule strikes a balance between collecting valuable data and minimizing participant burden, ensuring that study participation remains accessible and manageable. The structured weekly sessions, each featuring a different activity showcasing Rendever's VR product offerings, allow us to

assess the impact of VR on resident-adult child connection, well-being, and loneliness in a comprehensive manner.

To obtain evaluable data, minimum participation is defined as attending at least 3 of the 4 sessions, ensuring adequate exposure to the intervention for meaningful analysis. This threshold accounts for expected variability in participation, such as participant travel, hospitalizations, or changes to health, while maintaining the study's ability to detect potential effects.

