4.4 End-of-Study Definition

A participant is considered to have completed the study if he or she has completed the baseline (T1), four technology sessions (T2-T5), post-study survey (T6), and follow-ups at 1-month (T7) and 3-month (T8).

5 Study Population

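### Section 7.3 deems a temporarily unreachable participant withdrawn from the study with no route to later assessments, which conflicts with 1.2 and 7.2 for anyone who later returns

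*Combined protocol and SAP*

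**What the plan says.** Section 7.3 sets two joint conditions. One is a missed visit: "A participant will be considered lost to follow-up if he or she fails to return for 1 scheduled visit". The other, which must also be met, is failed contact: "study staff are unable to contact the participant after at least 3 attempts". Before the status is assigned, staff are to try to make contact and "reschedule the missed visit within the next week". If that fails, "he or she will be considered to have withdrawn from the study with a primary reason of lost to follow-up". The section does not mention approaching the person again at a later time point, or reinstating someone who reappears.

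Section 1.2 has two relevant categories. Lost to follow-up covers people who became unreachable and missed at least one follow-up assessment. Intermittent missing covers people who missed one or more surveys but completed later ones, and of these it says: "These cases were not considered lost to follow-up and were retained in all analyses for which valid data were available". It presumes that such gaps reflect temporary non-response and not formal withdrawal.

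Section 7.2 lists loss to follow-up among the reasons for which an investigator is permitted, but not required, to discontinue a participant.

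Sections 9.3 and 9.4.1 keep participants in the primary analysis by assigned group whether or not they complete the intervention, and handle missing data by maximum likelihood.

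**The concern.** Withdrawal from the study is a stronger status than stopping the sessions. Staff who apply 7.3 as written would ordinarily close the record and send no further surveys. A participant who is silent for a time and would have answered later is then lost by rule and not by choice.

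The stake is the sustained-effect question. Hypothesis H1a concerns change over time as well as concurrent effects, and T8 is the only 3-month measurement. Intent-to-treat with maximum likelihood keeps the person in the analysis set, but it cannot recover outcomes that were never requested, and standard maximum likelihood assumes that the gaps are missing at random. Section 4.3 names travel, hospitalisation and health changes as expected causes of absence, so some gaps may be related to outcome.

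Two features make the trigger easier to meet than it looks. Adult children, half of the sample, answer online. Section 6.4 provides up to three reminders for an incomplete survey, and 7.3 asks for at least three contact attempts. Section 7.3 does not say whether an online survey counts as a scheduled visit. If it does, three unanswered routine reminders could be read as meeting the contact condition. Also, 1.2 discontinues the whole dyad when one member chooses to withdraw during the intervention phase. Whether a withdrawal deemed under 7.3 counts for this purpose is not stated; if it does, the partner's data collection ends too.

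**Working it through.** **Inputs.** Contact rule: 7.3. Missing-data categories and attrition counts: 1.2. Discontinuation reasons: 7.2. Primary-outcome time points: 6.1.2. Time-point labels T6 (post-study), T7 (1 month) and T8 (3 months): 1.3 and 4.4.

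**Step 1: reproduce the reported attrition.**
- Before the end of the intervention phase: (20 × 2 + 2) / 372 = 42 / 372 = 11.29%. Section 1.2 states 11.3%.
- Whole trial: (20 × 2 + 12) / 372 = 52 / 372 = 13.98%. Section 1.2 states 13.9%, which is truncated; rounding gives 14.0%.
- After the intervention phase: 52 − 42 = 10 individuals. That is 10 / 372 = 2.7% of those consented, or 10 / 330 = 3.0% of the 372 − 42 = 330 who remained.

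**Step 2: apply each section to one participant.** Take someone who does not complete T7, cannot be reached after at least three attempts, and would respond at T8.
- Under 7.3 the person is withdrawn after T7, and nothing provides for a T8 approach.
- Under 1.2 the status depends on what happens later: lost to follow-up if no later survey is completed, intermittent missing and retained if T8 is completed.
- Under 7.2 the investigator may discontinue the person or not.

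The status in 1.2 can be settled only if T8 is offered, and 7.3 read literally closes the person before that. For someone who misses a survey but can be contacted there is no conflict: 7.3 is never triggered and 1.2 applies alone.

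**Step 3: what closure forfeits.** Section 6.1.2 measures all primary outcomes at four key time points: baseline, 1 week, 1 month and 3 months after the intervention.
- Closed during the sessions: T6, T7 and T8 are not collected, 3 of the 4.
- Closed after missing T6: T7 and T8 are forfeited in addition to the missed T6.
- Closed after missing T7: T8 is forfeited.
- Closed after missing T8: nothing further is scheduled.

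**Step 4: bound the number affected.** The readable text gives no count for lost to follow-up. If everyone closed under 7.3 is counted in the attrition total, the number lies between 0 and 52 of 372 (at most 14.0%), because the total pools seven reasons. At most 10 of these closures fall after the intervention phase. The flow diagram in 1.2 was not available to me; if it gives counts by reason, they replace this ceiling.

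**The case against.** The case on the other side is substantial. Section 7.3 requires both a missed visit and failed contact, and asks staff to make every effort first. It sets no one-week deadline for withdrawal; a week is the target for rescheduling. It nowhere says that later surveys are withheld. The lost-to-follow-up category in 1.2 also turns on being unreachable, so the two sections largely agree. Health-related limitations such as hospitalisation have their own attrition category. Participants stay in the intent-to-treat analysis. Section 1.2 is written in the past tense and reports people who missed surveys and later completed others, which suggests that follow-up was in practice offered to at least some.

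Much of this stands. That later outcomes are not sought is an inference from the word withdrawn, not a statement in the text. The conflict is confined to people who were unreachable and then returned. No figure supports a particular rate of such cases. It does not remove the problem: the shared reference to being unreachable does not settle the returning case, the permissive wording of 7.2 is a further inconsistency with 7.3, and a past-tense summary does not alter the rule as written.

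A reader might also infer a conflict with 4.3, where "minimum participation is defined as attending at least 3 of the 4 sessions", and with 4.4, which requires all four sessions for completion. The documents do not support that. Section 4.3 defines evaluable exposure and 4.4 defines completer status. These are separate labels from contact status, and a person can be evaluable without being a completer. A participant who misses one session while travelling but can be reached is not withdrawn under 7.3, and 6.4 provides for rescheduling.

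**Conclusion.** The point holds in a limited form. Section 7.3 turns one missed visit plus failed contact into study withdrawal with no route to later assessments, and 1.2, 7.2 and 7.3 give different answers for a participant who is unreachable and later returns. Followed literally, 7.3 forfeits between one and three of the post-intervention primary-outcome assessments for a person closed before T8, always including the only 3-month measurement.

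The number affected is unknown and may be small: at most 52 of 372, and at most 10 after the intervention phase. The conclusion rests on reading withdrawal from the study in its ordinary sense, and the ceiling rests on everyone closed under 7.3 being counted in the reported attrition. The documents do not show that any participant was in fact denied a later survey, or that the results are biased. The change is still worth making, because it is cheap and the missing outcomes cannot be recovered in the analysis.

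**What to change.** In 7.3, code a missed visit or survey as missed, with the reason where known. Keep the participant active for outcome collection and offer every later scheduled assessment through T8, unless the participant asks to stop or the investigator withdraws them. Assign lost to follow-up only when the T8 window closes without a response; the documents define no such window, so one has to be stated. Use the same definition in 1.2 and 7.2. State whether an online survey counts as a scheduled visit, and whether a deemed withdrawal triggers the dyad rule in 1.2. The change concerns outcome collection only, not whether sessions continue.

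If data collection is complete, state which rule was applied in practice, and report how many people were closed under 7.3 without later assessments being offered, so that the attrition figure rests on one definition.

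The cost is rewording three sections and, where follow-up is still open, up to three further survey invitations (T6, T7, T8) per unreachable participant.
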